- a. Nurses will be identified using our centralized education directory that associates nurses with their designated departments and hospital floors. All nurses permanently assigned to one of the 21 included study floors will be included in this study. Nurses who are not permanently associated with one of the 21 hospital floors (e.g. traveling nurse, float nurse) will be excluded from this study.

F. Randomization

- a. Nurses will be identified using our centralized education directory that associates nurses with their designated departments and hospital floors. Nurses will be cluster randomized by floor to receive one of two education modules about VTE prevention. Because of known differences between medical and surgical floors in VTE prophylaxis administration practice and culture, floors were stratified by department (i.e. medicine and surgery) for randomization. Within strata, we will use a coin toss to randomize floors into study arms.

G. Duration of Study

- a. Nurses will be given three months to complete the assigned education module. Data will be collected for one full year to include medication administration practice at baseline, during the education trial, and after the education trial.

H. Outcomes

- a. Primary Outcome measure: Proportion of non-administered doses of pharmacological VTE prophylaxis (dose level)
- b. Secondary Outcome Measures:
 - i. Nurse-reported relevance of and satisfaction with the education modules
 - ii. Proportion of doses documented as missed due to patient refusal (dose level)
 - iii. Proportion of patients with any VTE (patient level)
 1. VTE are defined by AHRQ PSI-12 diagnosis codes
 - iv. Proportion of patients with Deep Vein Thrombosis (DVT) (patient level)
 - v. Proportion of patients with Pulmonary Embolism (PE) (patient level)

Patient demographic data will be extracted from the Johns Hopkins Hospital administrative database. Pharmacologic VTE prophylaxis medication administration data will be extracted directly from electronic medication administration record in our computerized provider order entry system. Immediately following completion of the assigned education module, nurses will be asked to complete a voluntary 5-question survey to assess the relevance of and satisfaction with the education module.

3. Analytic methods

A. Baseline Characteristics

- a. Comparison of both arms to ensure similarity at baseline

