- b. Descriptive analysis of baseline characteristics i.e. simple counts and proportions by trial arm

B. Multi-level mixed effects linear regression

Due to the complexity of the multilevel structure of the data (i.e. multiple doses per patient across various hospitalizations, nurses and floors), multiple imputation¹⁹ will be used to reduce the levels of hierarchical structure to the floor level and nurse level by randomly selecting one dosage per patient. By reiterating the procedure 1000 times, we will estimate the odds ratios (ORs) and 95% confidence intervals conditional on the floor and nurse.

- a. Primary analyses: Intent-to-Treat
- b. Secondary analyses
 - i. Per protocol: Nurses who complete the education where the date of completion serves as an individual inflection point for pre-post education
 - ii. Nurse-reported relevance of and satisfaction with the education modules will be analyzed using a two-sided Chi-squared test

References

1. US Department of Health and Human Services. The Surgeon General's Call to Action to Prevent Deep Vein Thrombosis and Pulmonary Embolism. <http://www.ncbi.nlm.nih.gov/books/NBK44178/>. Accessed April 5, 2014.

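### If the nurse survey items have three or more ordered answers, the planned Chi-squared test ignores the order and gives no directional estimate; a mixed proportional-odds model with floor would be a cheap improvement

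*Combined protocol and SAP*

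**What the plan says.** Section 2.H lists "Nurse-reported relevance of and satisfaction with the education modules" as the first secondary outcome. On its collection, the same section says that on finishing the module "nurses will be asked to complete a voluntary 5-question survey to assess the relevance of and satisfaction with the education module". The whole analysis plan for it is the sentence in section 3.B.b.ii: "Nurse-reported relevance of and satisfaction with the education modules will be analyzed using a two-sided Chi-squared test".

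The text available for review, whose opening part is missing, does not give:
- the response format or number of answer categories
- a cut-point for collapsing answers
- the kind of Chi-squared test (all categories, 2x2, or trend)
- an effect measure or confidence interval for this outcome
- the number of nurses or the expected response rate.

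On the design, section 2.F states: "Nurses will be cluster randomized by floor to receive one of two education modules about VTE prevention", with floors stratified by department. Section 2.E adds: "All nurses permanently assigned to one of the 21 included study floors will be included in this study". For the dose-level outcomes, by contrast, section 3.B does name an effect measure and respects the clustering: "we will estimate the odds ratios (ORs) and 95% confidence intervals conditional on the floor and nurse".

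**The concern.** Relevance and satisfaction are usually recorded in degrees. If they are here, the natural comparison between the Dynamic and Static modules is whether one is rated higher, and by how much. An unordered Chi-squared test on k categories returns the same p-value however the categories are shuffled. It spreads its sensitivity over k-1 degrees of freedom, so it is less likely than an ordered test to detect a general shift towards better ratings. It can also be significant because opinions in one arm are merely more spread out. Collapsing to two groups restores a direction but discards information, and with no stated cut-point the choice is left open until the data are seen.

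At stake is a less efficient and less interpretable answer for one secondary outcome.

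**Working it through.** **No stated figure to reproduce.** The documents give no sample size, power, effect size or scale for the survey. Everything below is conditional on assumptions, which are labelled.

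**Inputs.** From the documents: a Chi-squared test called two-sided (3.B.b.ii), 5 voluntary questions (2.H), and 21 floors as the randomised units (2.E, 2.F). Assumed: a two-sided 5% level, in line with the 95% intervals planned in 3.B; a 5-point or 3-point item; the baseline distributions; an odds ratio (OR) of 1.5 or 2.0; respondents per arm; and independent nurses for the power comparison.

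**Step 1. One case by hand.** Take baseline p = 10/20/40/20/10%. A proportional-odds shift divides each cumulative odds by the OR. The cumulative odds are 0.111, 0.429, 2.333 and 9. Dividing by 1.5 gives 0.074, 0.286, 1.556 and 6, so the cumulative probabilities are 0.069, 0.222, 0.609 and 0.857, and q = 6.9/15.3/38.6/24.8/14.3%.

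The noncentrality with n per arm is λ = n × Σ(p − q)²/(p + q).
- The five terms are 0.0057, 0.0062, 0.0002, 0.0052 and 0.0076, with sum 0.0249.
- At n = 200, λ = 200 × 0.0249 = 4.98.
- On 4 degrees of freedom (critical value 9.49), power is about 40%.
- If the same λ is carried by 1 degree of freedom, power is about Φ(√4.98 − 1.96) = Φ(0.27) = 61%.

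Simulation (4,000 runs) gives 39.7% for the 5-category Chi-squared and 60.8% for the tie-corrected rank-sum test. The loss therefore comes from spending 4 degrees of freedom on what is essentially a one-dimensional shift.

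**Step 2. Range of assumptions.** Simulated power, 5-category Chi-squared → rank test:

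| Baseline | OR | 100/arm | 200/arm | 300/arm |
|---|---|---|---|---|
| 10/20/40/20/10% | 1.5 | 21 → 35% | 40 → 61% | 57 → 78% |
| 10/20/40/20/10% | 2.0 | 55 → 77% | 89 → 97% | 98 → 99.8% |
| 2/5/13/40/40% | 1.5 | 18 → 32% | 35 → 59% | 54 → 76% |
| 2/5/13/40/40% | 2.0 | 50 → 73% | 84 → 95% | 96 → 99% |

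For a third 5-level baseline (5/10/20/40/25%, OR 1.5), power is 29 → 48% at 150 per arm, 48 → 70% at 250 and 65 → 84% at 350. With 3 levels (20/45/35%, OR 1.5) it is 38 → 47%, 57 → 68% and 73 → 82%. With no difference, all tests held about 5%.

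At moderate power the loss is about 9 to 11 points with 3 levels and 14 to 23 with 5. At OR 2.0 and 300 per arm it is only 2 to 3 points.

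**Step 3. Collapsing to the top two levels.** At OR 1.5 and 200 per arm, the 2x2 test has 49% power on the symmetric baseline and 33% on the ceiling baseline, against 61% and 59% for the rank test.

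**Step 4. Yes/no items.** For 60/100 against 75/100, Chi-squared gives p = 0.0235 and the rank test p = 0.0239. There is practically no difference.

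**Step 5. Spread only.** This is a constructed case: 5/20/50/20/5% against 12/20/36/20/12%, 250 per arm. Here λ = 250 × (2 × 0.07²/0.17 + 0.14²/0.86) = 250 × 0.0804 = 20.1. In simulation, Chi-squared is significant 97% of the time and the rank test 5%, with neither arm centred higher.

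**Step 6. Does an ordered test suffice by itself?** No. Assume 11 against 10 floors, 20 responders per floor and an ICC of 0.05. The design effect is 1 + 19 × 0.05 = 1.95. Type I error of tests that treat nurses as independent is then about 16% (2x2 Chi-squared), 28% (5-category Chi-squared) and 15% (rank test). Over 10 to 40 responders per floor and ICCs of 0.01 to 0.10, the 2x2 test ranges from about 6% to 38%. An ordered analysis that omits floor keeps this problem.

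**The case against.** The strongest objection is that graded answers are nowhere stated. The items may be yes/no, or answers may be collapsed before testing. The words 'two-sided' could even hint at a 2x2 comparison, or be routine phrasing. That stands, and it makes the point conditional. That the proposed model also suits yes/no items shows that the change is safe, not that the planned test is wrong.

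A reader might infer that the planned test cannot show which module is rated better. The documents do not support that. A 2x2 table has a direction, and in a larger table the percentages by arm still show it. Only the omnibus p-value is non-directional.

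A reader might also infer that the trial will probably miss a real difference in ratings. That is not supported either. The power figures assume independent nurses and invented sample sizes and effects, so they compare the efficiency of tests and do not predict this trial. With responses correlated within floors, a test that ignores floor errs towards false positives.

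Finally, both hypotheses in the plan concern missed doses, and no superiority hypothesis is stated for the survey. That also stands, and it keeps the severity low.

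**Conclusion.** The point holds conditionally. If the items have three or more ordered answers and are analysed uncollapsed, the one test named in 3.B.b.ii loses roughly 10 to 20 percentage points of power against a shift when power is moderate. It loses little when power is already high and nothing for yes/no items. Its p-value then has no direction, and the plan names no odds ratio, difference or interval to supply one.

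The size rests on an assumed scale, baseline distribution, effect, number of respondents and independence between nurses. The documents supply none of these. The sentence cannot be called an error as it stands, because the scale is unknown. It can be improved at almost no cost, provided that the replacement accounts for floors. The primary outcome and both stated hypotheses are untouched.

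**What to change.** In 3.B.b.ii, state the response scale of the five items and replace the Chi-squared test with a cumulative-logit (proportional-odds) model of the uncollapsed ratings:
- arm and department (the randomisation stratum) as fixed effects
- floor as a random effect, required because floors are the randomised units
- the Dynamic-versus-Static odds ratio of a higher rating, with its 95% CI, as the reported result
- a table of raw percentages in each answer category by arm.

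For yes/no items the same model is mixed-effects logistic regression, so the wording works for either format.

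The cost is a sentence or two in the SAP and no new data. The small downside is the proportional-odds assumption, which a difference in spread like that in step 5 would violate; the table of percentages lets readers judge it.
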